8.2.4 Clinical safety laboratory assessments

- See Appendix 2 ([Section 10.2](#)) for the list of clinical laboratory tests to be performed and to the SoA for the timing and frequency.
- The Investigator must review the laboratory report, and document this review.
 - All protocol-required laboratory assessments, as defined in Appendix 2 ([Section 10.2](#)), must be conducted in accordance with the laboratory manual and the SoA.
 - If laboratory values from non-protocol specified laboratory assessments performed at the institution's local laboratory require a change in participant management (eg, SAE or leading to dose modification), then the results must be recorded in the eCRF.
 - Liver function tests Grade ≥ 3 during participation in the study or within 30 days after the last dose of study intervention should be repeated until the values return to normal or baseline. If such values do not return to normal/baseline within a period of time judged reasonable by the Investigator, the etiology should be identified and the Sponsor notified if it is not considered to be related to the underlying disease.

8.3 ADVERSE EVENTS AND SERIOUS ADVERSE EVENTS

Adverse event of special interest

An adverse event of special interest (AESI) is an AE (serious or nonserious) of scientific and medical concern specific to the Sponsor's product or program, for which ongoing monitoring and immediate notification by the Investigator to the Sponsor is required. Such events may require further investigation in order to characterize and understand them. Adverse events of special interest may be added, modified or removed during a study by protocol amendment.

- Pregnancy occurring in a female participant entered in the clinical trial. It will be qualified as an SAE only if it fulfills one of the seriousness criteria (see Appendix 3 [[Section 10.3](#)]).
 - In the event of pregnancy in a female participant, IMP should be discontinued.
 - Follow-up of the pregnancy in a female participant is mandatory until the outcome has been determined (See Appendix 4 [[Section 10.4](#)]).

- Symptomatic overdose (serious or nonserious) with IMP.
 - An overdose (accidental or intentional) with the IMP is an event suspected by the Investigator or spontaneously notified by the participant (not based on systematic pills count) and defined as at least twice the intended dose within the intended therapeutic interval, adjusted according to the tested drug.
 - Of note, asymptomatic overdose has to be reported as a standard AE.
- Increase in alanine transaminase (ALT) \geq Grade 2.
 - Liver function tests should be performed in patients with onset of otherwise unexplained nausea, jaundice, right upper abdominal pain, fever, or rash. LFTs include AST, ALT, ALP (isoenzymes if increase in ALP \geq Grade 3), total bilirubin (direct bilirubin if total bilirubin $>2 \times$ ULN), GGT, and INR (if total bilirubin $>2.5 \times$ ULN).
 - Discontinue study intervention in case of increase in ALT \geq Grade 2 if still on treatment, and repeat Liver function tests (LFTs) within 2-3 days. If not recovered, monitor LFTs weekly until recovery to Grade ≤ 1 (or baseline grade). Confounding factors such as, hepato-biliary disorders, concomitant medications, etc. should be excluded prior to study treatment discontinuation.
 - An ultrasound or other imaging in liver should be considered based on the clinical presentation.
 - A consultation with a hepatologist should be undertaken if there is,
 - unexplained or persistent increase in ALT \geq Grade 3 despite study treatment discontinuation.
 - ALT $>3 \times$ ULN and concomitant jaundice (total bilirubin $>2.5 \times$ ULN), in patients with normal ALT and total bilirubin at baseline.
 - to exclude hepato-biliary disorders (eg, hepatotropic virus infections, autoimmune or alcoholic hepatitis, Non-Alcoholic Steatohepatitis, etc) or drug induced liver injury.
 - Further hepatic virology will be undertaken as per the site's local guidelines for the treatment of cancer patients, taking into account the local and national recommendations.
- Photosensitivity
 - If photosensitivity reaction is suspected in study participants, consider dermatologist consultation. Confounding factors such as other dermatological disorders, drug eruptions resulting from concomitant medication use, etc should be excluded prior to discontinuation of amcenestant. In case of amcenestant discontinuation because of photosensitivity reaction, study participant should be followed for possibility of development of other manifestations of phototoxicity such as photo-onycholysis, lichenoid reaction or actinic granuloma.

The definitions of an AE or SAE can be found in Appendix 3 ([Section 10.3](#)).

AE will be reported by the participant (or, when appropriate, by a caregiver, surrogate, or the participant's legally authorized representative).

The Investigator and any qualified designees are responsible for detecting, documenting, and recording events that meet the definition of an AE or SAE and remain responsible for following up AEs that are serious, considered related to the study intervention or study procedures, or that caused the participant to discontinue the study intervention (see [Section 7](#)).

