8.3 AEs and SAEs	Added phototoxicity reaction in AESI.	Preclinical toxicity studies using amcenestant indicated a potential risk for phototoxicity. Therefore, photosensitivity has been added as an AESI in order to collect additional relevant information of these events.
8.3 AEs and SAEs & 6.6 Dose Modification (Table 3)	Added guidance on the management of Increase in alanine transaminase (ALT) \geq Grade 2.	As the study IMPs have a potential to induce hepatic toxicity, the implemented changes are added as part of risk minimization strategy.
8 Study Assessment and Procedure; & 10.1.6 Data quality assurance & 10.14 Appendix 14: Contingency measures for a regional or national emergency that is declared by a governmental agency	Added new section describing the contingency measures for a regional or national emergency that is declared by a government agency.	These measures have been added to help manage the study conduct during an emergency (eg, COVID-19 pandemic).
1.1 Synopsis: primary analysis & 9.4.1.1 Analysis of primary endpoint	Changed the statistical model from t-test to analysis of covariance (ANCOVA) model.	To add baseline Ki67 as a covariate when comparing the Ki67 log-proportional change after a 14-day treatment period between treatment groups.
10.13 Appendix 13 Abbreviated modification of diet in renal disease formula	Updated the formula of eGFR calculation. Provided a linkage of eGFR calculator.	To provide site with a calculator for eGFR based on creatinine in 2 different units.
10.15 Appendix 15: Protocol amendment history	Summary of Changes in Amendment 01 was captured.	Summary of protocol history is mandated.
Throughout the Document	Added the INN name amcenestant. And Performed administrative and editorial updates and corrections.	INN name was obtained. And to improve consistency and clarity.
Throughout the amended protocol	Performed administrative and editorial updates and corrections.	To improve consistency and clarity.

TABLE OF CONTENTS

AMENDED CLINICAL TRIAL PROTOCOL 02	1	
PROTOCOL AMENDMENT SUMMARY OF CHANGES	2	
DOCUMENT HISTORY	2	
OVERALL RATIONALE FOR THE AMENDMENT	2	
TABLE OF CONTENTS	5	
LIST OF TABLES	9	
LIST OF FIGURES	9	
1	PROTOCOL SUMMARY	10
1.1	SYNOPSIS	10
1.2	SCHEMA	15
1.3	SCHEDULE OF ACTIVITIES (SOA)	16
2	INTRODUCTION	20
2.1	STUDY RATIONALE	20
2.2	BACKGROUND	21
2.3	BENEFIT/RISK ASSESSMENT	21
3	OBJECTIVES AND ENDPOINTS	22
3.1	APPROPRIATENESS OF MEASUREMENTS	22
4	STUDY DESIGN	23
4.1	OVERALL DESIGN	23

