6.6 DOSE MODIFICATION

If a dose of IMP is vomited or omitted, the participant should not take the dose later or 2 doses at the next planned dose, and this information has to be recorded in the patient diary and eCRF.

Investigational medicinal product dose omission is allowed in case of severe toxicity and the reason should be documented in the eCRF. Doses omitted for toxicity are not to be replaced after the 14-day treatment period or compensated at the next planned IMP intake during the 14-day treatment period.

Conditions for dose modifications are aligned in [Table 3](#). Please refer to letrozole label information on additional specific contraindications and events requiring use precaution, and instruction of dose modification.

Table 3 - Dose modification for amcenestant arms and letrozole arm

NCI-CTCAE grade	Dose modifications
Grade 1 or 2	No dose adjustment required except for Grade 2 alanine transferase defined as an AESI *
Grade \geq 3	Amcenestant and letrozole should be definitely discontinued. No reintroduction is allowed.

NCI-CTCAE = National Cancer Institute Common Terminology Criteria for Adverse Events.

* See [Section 8.3](#)

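### Protocol 8.3 puts a confounder check before stopping drug for raised ALT; this conflicts with Table 3 at Grade 3 or higher and sets no time limit at Grade 2

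*Protocol*

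**What the plan says.** Protocol 8.3 makes an ALT increase of Grade 2 or higher an adverse event of special interest. The management bullet opens with "Discontinue study intervention in case of increase in ALT" of that grade if the participant is still on treatment, and asks sites to "repeat Liver function tests (LFTs) within 2-3 days", with weekly tests until recovery. It closes with: "Confounding factors such as, hepato-biliary disorders, concomitant medications, etc. should be excluded prior to study treatment discontinuation". That sentence is not limited to Grade 2. The bullet gives no time limit for the check, does not say whether dosing goes on during it, and gives no action if a confounder is found.

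Table 3 in Protocol 6.6 has two rows:
- Grade 1 or 2: "No dose adjustment required except for Grade 2 alanine transferase defined as an AESI". An asterisk on this exception points to 8.3.
- Grade 3 or higher: "Amcenestant and letrozole should be definitely discontinued. No reintroduction is allowed". This row has no pointer to 8.3 and no condition.

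The text of 6.6 also allows a dose to be omitted in case of severe toxicity, and adds: "Doses omitted for toxicity are not to be replaced after the 14-day treatment period".

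**The concern.** A site with a participant at ALT Grade 3 or higher has two written instructions. One orders a definitive stop. The other asks for a work-up before the stop and, read literally, implies no stop if another cause turns up. Neither section states which takes precedence.

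This is a participant-safety matter. The amendment summary explains the ALT guidance with the words "As the study IMPs have a potential to induce hepatic toxicity", and calls it part of a risk minimization strategy. Protocol 2.3 says that the study offers the patient no direct benefit, so there is no therapeutic gain to set against further doses taken while a liver signal is being explained. Sample size, alpha and power are not involved.

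**Working it through.** The plan gives no figure here to reproduce. The main check is to set the texts side by side; a short count of doses then gives the size.

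**1. Grade 3 or higher.** The 8.3 bullet covers Grade 2 or higher, so Grade 3 falls under it. Table 3 sends only Grade 2 ALT to 8.3, so nothing places the Grade 3 row under the confounder step.
- Check finished before the next daily dose, no confounder found: the participant stops, and both rules are met.
- Check runs past the next daily dose: 8.3 delays the stop, Table 3 does not. Conflict.
- Confounder found: 8.3 read literally gives no stop, Table 3 requires one. Conflict.

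**2. Grade 2.** Table 3 defers to 8.3, so there is no second rule to contradict. The bullet can be read as one conditional instruction: check the cause, then stop. Even so, dosing may continue for an unstated time. The dose-omission allowance in 6.6 is for severe toxicity. It does not clearly reach Grade 2 and is not tied to the ALT work-up.

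**3. What 8.3 assumes elsewhere.** One trigger for a hepatologist consultation is an ALT of Grade 3 or higher that is unexplained, or that persists, although treatment has been stopped. A listed purpose of that consultation is to rule out hepato-biliary disorders. So 8.3 itself expects that drug can be stopped before the cause is known, and places after the stop an exclusion that its closing sentence places before it.

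**4. When it can arise.** The Schedule of Activities (1.3) has chemistry at screening, a conditional pre-dose repeat at D1, and D14. There is none at D7. After the D14 dose no dose remains; at most the D14 dose itself is in play, if the result is back before it is taken. The case therefore arises mainly from the symptom-driven liver tests that 8.3 calls for.

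**5. Doses at stake.** Assume that the result is known after the dose on Day d and that no earlier dose was missed. Further doses possible with no time limit = 14 − d. The protocol gives no work-up length. I assume w = 2 or 3 days, borrowed from the repeat-test interval in 8.3, which the protocol ties to stopping and not to the work-up. Doses during the work-up = min(w, 14 − d).

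| Day d | Upper bound, 14 − d | During a 2–3 day work-up |
|---|---|---|
| 7 | 7 | 2–3 |
| 10 | 4 | 2–3 |
| 11 | 3 | 2–3 |
| 12 | 2 | 2 |
| 13 | 1 | 1 |
| 14 | 0 | 0 |

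**6. Effect of a prompt stop on the analysis sets.** SAP 2.3.3 removes a participant with 10 or fewer treatment days from the per-protocol population. The SAP does not say how those days are counted. For a definitive stop after the dose on Day d, counting dosing days gives d, and so does the exposure formula in SAP 2.4.4 (last dose date − first dose date + 1). A stop on Day 10 or earlier is therefore excluded on either count, and a stop on Day 11 or later is not. Protocol 7.1.1 keeps the post-treatment biopsy as scheduled after an early stop, so a participant with Ki67 values from both biopsies stays in the mITT population.

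**The case against.** The strongest reply is that the bullet states a deliberate, conditional rule. The photosensitivity paragraph in 8.3 uses the same construction (confounders "should be excluded prior to discontinuation of amcenestant"), which suggests that check-then-stop was intended. This stands for Grade 2: a reader might call the bullet self-contradictory there, but the text does not force that. What remains at Grade 2 is the missing time limit.

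A reader might also infer that a site can never obey both rules while the cause is open. That goes too far. Dosing is once daily, and a same-day review of history and concomitant medication, followed by a stop before the next dose, satisfies both.

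Several provisions limit the risk. ALT, AST or bilirubin above 1.5 × ULN excludes entry (E14). These events are reported within 24 hours (8.3.1). The investigator may stop treatment at any time (7.1.1). Section 6.6 permits omission for severe toxicity, which could serve as an interim hold in severe cases. Both stopping rules are worded as recommendations. All of this makes prolonged dosing less likely, but none of it says which rule governs at Grade 3 or higher, or whether a Grade 2 participant takes the next dose during the work-up.

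**Conclusion.** The point holds in this form: a conflict at ALT Grade 3 or higher when a confounder is found or the check outlasts the dosing interval, and at Grade 2 a gap in timing, not a contradiction. It deserves correction because it is a safety instruction and the remedy is one sentence.

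Its reach is small. Under the assumed 2 to 3 day work-up, 2 to 3 doses are at stake for a result known by Day 11, falling to none after the Day 14 dose. The 14 − d column is only a ceiling. A reader might take it to mean that the protocol directs dosing through to Day 14, but the bullet's opening sentence and the investigator's discretion both point the other way. The documents give no expected frequency of ALT Grade 2 or higher, so the number of participants affected cannot be estimated. Nor do they support reading this as a threat to the primary result, since the biopsy is still taken.

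**What to change.** Keep the opening sentence of the 8.3 ALT bullet (discontinue at Grade 2 or higher if still on treatment). Replace the closing sentence with:

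*Confounding factors such as hepato-biliary disorders and concomitant medications should be investigated after IMP is stopped; stopping must not be delayed for this work-up. At Grade 3 or higher, discontinuation is definitive per Table 3.*

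Section 6.6 and Table 3 then need no edit: the Grade 2 row already points to 8.3, and the Grade 3 row already says what is wanted. A Grade 2 hold with later resumption would be a worse choice, because it would clash with the retained instruction to discontinue and would need a restart rule that 8.3 does not have.

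The administrative cost is a protocol clarification or a letter to sites. The clinical cost is that a few participants whose ALT rise has another cause will miss their remaining doses (14 − d of them), which are not made up. Those who stop on Day 10 or earlier leave the per-protocol population, which serves only sensitivity analysis.

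SAP 2.4 records that enrolment ended early. If dosing is complete, what remains is to document in the study report how any ALT Grade 2 or higher cases were handled.

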8.3.1 Time period and frequency for collecting AE and SAE information

All AEs and SAEs will be collected from the signing of the informed consent form (ICF) until the follow-up visit at the time points specified in the SoA ([Section 1.3](#)).

All SAEs and AESI will be recorded and reported to the Sponsor or designee immediately and under no circumstance should this exceed 24 hours, as indicated in Appendix 3 ([Section 10.3](#)). The Investigator will submit any updated SAE data to the Sponsor within 24 hours of it being available.

Investigators are not obligated to actively seek AE or SAE after conclusion of the study participation. However, if the Investigator learns of any SAE, including a death, at any time after a participant has been discharged from the study, and he/she considers the event to be reasonably related to the study intervention or study participation, the Investigator must promptly notify the Sponsor.

8.3.2 Method of detecting AEs and SAEs

The method of recording, evaluating, and assessing causality of AE and SAE and the procedures for completing and transmitting SAE reports are provided in Appendix 3 ([Section 10.3](#)).

Care will be taken not to introduce bias when detecting AEs and/or SAEs. Open-ended and non-leading verbal questioning of the participant is the preferred method to inquire about AE occurrences.

8.3.3 Follow-up of AEs and SAEs

After the initial AE/AESI/SAE report, the Investigator is required to proactively follow each participant at subsequent visits/contacts. All SAEs, and non-serious AEs of special interest (as defined in [Section 8.3](#)), and non-serious AEs related to IMP still ongoing at the pre-specified study end-date, will be followed until resolution, stabilization, the event is otherwise explained, or the participant is lost to follow-up (as defined in [Section 7.3](#)). Further information on follow-up procedures is given in Appendix 3 ([Section 10.3](#)).

8.3.4 Regulatory reporting requirements for SAEs

- Prompt notification by the Investigator to the Sponsor of a SAE is essential so that legal obligations and ethical responsibilities towards the safety of participants and the safety of a study intervention under clinical investigation are met.

- The Sponsor has a legal responsibility to notify both the local regulatory authority and other regulatory agencies about the safety of a study intervention under clinical investigation. The Sponsor will comply with country-specific regulatory requirements relating to safety reporting to the regulatory authority, Institutional Review Boards (IRB)/Independent Ethics Committees (IEC), and Investigators.
- Investigator safety reports must be prepared for suspected unexpected serious adverse reactions (SUSAR) according to local regulatory requirements and Sponsor policy and forwarded to Investigators as necessary.
- Adverse events that are considered expected will be specified in the reference safety information.
- An Investigator who receives an Investigator safety report describing a SAE or other specific safety information (eg, summary or listing of SAEs) from the Sponsor will review and then file it along with the Investigator's Brochure and will notify the IRB/IEC, if appropriate according to local requirements.

8.3.5 Pregnancy

- Details of all pregnancies in females will be collected after the signing the ICF until outcome of pregnancy (See Appendix 4 [[Section 10.4](#)]).
- If a pregnancy is reported, the Investigator should inform the Sponsor within 24 hours of learning of the pregnancy and should follow the procedures outlined in Appendix 4 ([Section 10.4](#)).
- Abnormal pregnancy outcomes (eg, spontaneous abortion, fetal death, stillbirth, congenital anomalies, ectopic pregnancy) are considered SAEs.

8.3.6 Guidelines for reporting product complaints

Any defect in the IMP must be reported as soon as possible by the Investigator to the monitoring team that will complete a product complaint form within required timelines.

Appropriate information (eg, samples, labels or documents like pictures or photocopies) related to product identification and to the potential deficiencies may need to be gathered. The Investigator will assess whether or not the quality issue has to be reported together with an AE or SAE.

8.4 TREATMENT OF OVERDOSE

The Sponsor does not recommend specific treatment for an overdose.

In the event of an overdose (as defined in [Section 8.3](#)), the Investigator should:

1. Contact the Medical Monitor immediately.
2. Closely monitor the participant for any AE/SAE and laboratory abnormalities until IMP can no longer be detected systemically (at least 7 days for amcenestant and 5 times the half life time of letrozole from the date of overdose).

3. Obtain a plasma sample for PK analysis within 7 days from the date of the last dose of study intervention if requested by the Medical Monitor (determined on a case-by-case basis).
4. Document appropriately in the CRF.

Decisions regarding dose interruptions or modifications will be made by the Investigator in consultation with the Medical Monitor based on the clinical evaluation of the participant.

8.5 PHARMACOKINETICS

- Pharmacokinetic sampling is planned only in participants randomized in amcenestant treatment arms.
- Blood samples of approximately 1 mL will be collected for measurement of plasma concentrations of amcenestant as specified in the SoA ([Section 1.3](#)) using a validated liquid chromatography-mass spectrometry/mass spectrometry assay. Instructions for the collection and handling of PK samples will be provided by the Sponsor in the laboratory manual.
- Samples will be used to evaluate the PK of amcenestant. Samples collected for analyses of amcenestant plasma concentration may also be used to evaluate safety or efficacy aspects related to concerns arising during or after the study.
- It is of utmost importance to collect all blood samples at the specified time windows and according to the specifications (refer to the laboratory manual).
- Samples missed or lost for any reason should be recorded. Actual dates and times (24-hour clock time) of blood collection should be recorded. Actual dates and times of previous drug administration should also be precisely recorded.

For the comfort of the participants, some PK samplings may be deleted during the course of the study if they are no longer deemed necessary by the Sanofi PK team.

Any changes in the timing or addition of time points for any planned study assessments must be documented and approved by the relevant study team member and then archived in the Sponsor and site study files but will not constitute a protocol amendment. The IRB/IEC will be informed of any safety issues that require alteration of the safety monitoring scheme or amendment of the ICF.

